1.0 PROTOCOL SUMMARY AND/OR SCHEMA

The primary objective of the study is to determine the maximum tolerated dose (MTD) of rucaparib in combination with breast and nodal radiotherapy (RT) in women with triple negative breast cancer (TNBC) with residual disease following neoadjuvant chemotherapy or high grade hormone receptor (HR) positive disease with high volume residual following neoadjuvant chemotherapy. Secondary objectives are to describe the toxicities and disease outcomes and to identify biomarkers of locoregional relapse following rucaparib plus RT.

[figure not shown]
This is an amended protocol in which we add additional negative dose escalation levels to allow probing of the MTD into lower doses of rucaparib. In the original design, we had one -1 dose level, but we have exceeded the observed DLT for the TITE-CRM threshold at this level (see Biostatistics, section 14). We now add 3 additional de-escalation (-2, -3, and -4 dose levels). It is not surprising that even low dose levels of a PARP inhibitor may have radiosensitizing effects; for this reason we add 3 additional de-escalations.

Eligibility criteria include stage I-III TNBC patients with residual invasive disease following neoadjuvant chemotherapy (NAC), as well as high grade HR positive disease with high volume residual (4 or more positive axillary nodes, or 5 cm or more of residual breast disease) after NAC. Tumor tissue will be collected at the time of surgery, if available, precluding the need for an extraneous biopsy.

Treatment will consist of rucaparib at one dose level (200 mg QD, 300 mg QD, 200 mg BID, 300 mg BID, 400 mg BID, 500 mg BID, 600 mg BID) throughout a 6-week course of RT and then 4 weeks of maintenance rucaparib, at the same dose level, following RT. RT dose will consist of 50 Gy in 2 Gy/fraction to the breast or post-mastectomy chest wall, with or without nodes plus a 10 Gy boost to the lumpectomy cavity or (optionally) to the mastectomy scar (total dose 60 Gy). Patients will be followed for evaluation of toxicity with weekly assessments during the 10-week study period. For post-mastectomy patients not treated with a boost (ie only 5 weeks of radiation), rucaparib will be continued for 4 weeks post-RT for a total of 9 weeks. Patient-reported outcomes will be assessed and subject drug diaries will be maintained. Patients will then be followed every 3-6 months for two years, as per standard follow-up care.

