The trial will be monitored using a TITE-CRM (Time-To-Event Continual Reassessment Modulation) design¹. The target rate for dose-limiting toxicity (DLT) is 30%. DLT will be defined as toxicities probably or definitely related to the study drug observed during the study period. A detailed definition of dose-limiting toxicity (DLT) for this trial is defined in Section 9.5.

The target accrual is 30 patients, to be accrued within 2 years.

- Radiation dose is 50 Gy/25 fractions to the whole breast or chest wall +/- regional nodes plus a 10 Gy/5 fractions boost to the lumpectomy cavity. Mastectomy patients may also receive scar boosts; rucaparib will continue for 4 weeks post-RT (total of 9-10 weeks depending on whether a boost is used).
- Tumor tissue will be procured from the lumpectomy or mastectomy specimens, as well as from the baseline diagnostic cores, if available.

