9.0 TREATMENT/INTERVENTION PLAN

9.1 Rucaparib Administration

Rucaparib will be administered concurrently with radiotherapy, commencing on the evening following the first radiation treatment, and then twice daily throughout the standardized 6-week course of radiation treatment to the breast with or without regional nodes. Subjects will receive rucaparib at their assigned dose level, beginning with dose level 0. Subjects will be instructed to take rucaparib as morning and evening doses, separated by approximately 12 hours, at the same time each day (BID dosing). Rucaparib treatment will be continued throughout the course of RT, including weekends or holidays when radiation fractions may not be administered. Rucaparib administration will continue for four weeks after the final fraction of RT.

Treatment will be administered on an outpatient basis. Subjects will receive sufficient quantities of capsules of rucaparib for administration every 2 weeks over the study duration. Subjects will be provided self-administration instructions and subject drug diaries to record the date and time study drug was taken. Subjects will be instructed to store study drug according to the label, subjects should return all study drug bottles and their drug diaries at their study visits.

Daily oral rucaparib should be taken with a glass of water, with or without a meal. Tablets should be swallowed whole without crushing or chewing. In case of vomiting after a dose of rucaparib, the dose should not be re-administered. If a patient misses a dose and less than 4 hours have passed since the scheduled dose time, the dose should be immediately taken. If more than 4 hours have passed since the scheduled time, the subject should not take the missed dose and wait to take the next scheduled dose.

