9.5 Definition of Dose-Limiting Toxicity

Dose-limiting toxicity (DLT) will be defined as toxicities probably or definitely related to the study drug observed during the 70 days that include 6 weeks of radiotherapy and 4 weeks of maintenance rucaparib therapy, as follows:

- Confluent moist desquamation, defined as the presence of a single, contiguous region of moist desquamation that exceeds 25 cm² in area
- Absolute Neutrophil Count <1,000/mm³, with or without fever
- Platelet count <50,000/mm³
- Hemoglobin <8.0 g/dl
- Any ≥ Grade 3 non-hematologic toxicity by the NCI CTCAE version 4.03, not including Grade 3 ALT/AST elevation provided bilirubin and alkaline phosphatase meet criteria in Section 11.2
- Any toxicity requiring a RT dose delay exceeding 5 business days

Toxicities meeting this definition and occurring during the observation period of 10 weeks (70 days) will influence the dose level assignment of the TITE-CRM algorithm if these toxicities are deemed probably or likely related to study therapy.

Sites should contact the coordinating center as soon as possible (within one business day) when a DLT occurs or seems imminent. Sites should call [name] [name], and send an email to [name] [name] and study coordinator.

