9.7 Study Duration

Treatment is expected to continue for a total of ten weeks (70 days), as described, unless delayed by adverse events, or discontinued due to meeting criteria described in Section 13.1

Following the ten week course of study treatment, follow up visits will continue every 3-6 months for two years, or as per standard follow-up care. Participants removed from study for unacceptable adverse events will be followed until resolution or stabilization of the adverse event.

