11.2 Dose Modifications

Radiation therapy may be withheld due to acute toxicity at the discretion of the treating investigator without being considered a dose-limiting toxicity if the treatment break is no greater than 5 days. All radiation treatment breaks should be recorded, including details regarding duration of break and reason.

Rucaparib dose will not be modified on this study. Treatment with rucaparib should be held if any of the following are observed:

Table 11B

Toxicity	Rucaparib Treatment Action	Timing for Restarting Rucaparib Treatment
----------	----------------------------	-------------------------------------------

Confluent moist desquamation (single, contiguous region of moist desquamation that exceeds 25cm ² in area)	Record DLT	Discontinue rucaparib
Any toxicity requiring a radiotherapy dose delay exceeding 5 business days	Record DLT	Discontinue rucaparib
Grade 3 or 4 hematologic toxicity Includes defined DLTs: Absolute Neutrophil count <1,000/mm ³ (with or without fever) Platelet count <50,000/mm ³ Hemoglobin <8.0 g/dl	Record DLT	Discontinue rucaparib
Grade 3 or 4 non-hematologic toxicity Except for: 
• alopecia, nausea, vomiting, or diarrhea adequately controlled with systemic antiemetic/antidiarrheal medication administered in standard doses according to the study center routines• Grade 3 ALT/AST elevation (see below)	Record DLT	Discontinue rucaparib
Grade 4 ALT/AST elevations	Hold rucaparib	Restart treatment when values have returned to ≤ Grade 2. Monitor liver function tests weekly for 3 weeks after reintroduction of rucaparib. Any toxicity requiring a radiotherapy dose delay exceeding 5 business days should be recorded as a DLT and rucaparib discontinued.

Grade 3 ALT/AST elevations	Continuation of rucaparib with elevation of ALT/AST up to Grade 3 is permitted provided: 
• bilirubin is < ULN• alkaline phosphatase is < 3x ULNand• there are no other signs of liver dysfunction	Monitor liver function tests weekly until resolution to ≤ Grade 2. If patient has Grade 3 ALT/AST and continues on rucaparib, and levels do not decline within 2 weeks or they continue to rise, treatment interruption and resolution to ≤ Grade 2 will be required before rucaparib can be resumed at current dose.

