Grade 2 toxicity not adequately controlled by concomitant medications and/or supportive care.	Hold rucaparib upon investigator discretion	Restart drug, per investigator discretion, at assigned study dose level (no dose reduction). Note: any toxicity requiring a radiotherapy dose delay exceeding 5 business days should be recorded as a DLT and rucaparib discontinued. Drug holds exceeding 5 business days will be reviewed by the PI and discussed by the study team and the treating physicians. If the patient restarts Rucaparib after a break, missed doses will not be made up. The patient will take Rucaparib until the conclusion of the initially scheduled 10 weeks.

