14.0 BIOSTATISTICS

The primary endpoint of the study is defining the MTD of rucaparib in combination with RT to the breast/ chest wall with or without regional nodes.

The trial will be monitored using TITE-CRM. Assuming a model for the time to occurrence of toxic response as a function of dose, the method allows information from all enrolled patients to be used when allocating a new patient to a dose level. Subjects can be continuously recruited throughout the trial, as long as patients are treated at a dose consistent with the current safety profile.

The definition of dose-limiting toxicity (DLT) for this trial is defined in Section 9.5 above.

The acute observation period for toxicity is defined as 10 weeks, which includes the 6-week rucaparib and radiotherapy treatment course and a 4-week post RT rucaparib maintenance period.

The target rate for dose-limiting toxicity is 30%. This level was selected upon rates of toxicity observed in a recent phase I study of veliparib + chest wall RT in breast cancer patients [14]. The target rate will define the maximum tolerated dose (MTD) of rucaparib given concurrently with radiotherapy for residual invasive disease after neoadjuvant chemotherapy.

The expected rates of acute toxicity have been estimated based upon previous treatment experience with radiotherapy for these indications, and clinically acceptable maximal levels of toxicity. These rates will be re-estimated throughout the conduct of this trial as treatment experience is accrued.

Dose allocation

Phase I dose levels corresponding to expected toxicity rates are presented in the following table. Rucaparib will be escalated in this protocol as shown below, concurrently with a standard radiotherapy treatment plan, delivered in 2 Gy fractions, 5 days a week, over 5-6 weeks, delivered to the breast or chest wall with or without regional nodal basins.

Intrasubject escalation of the rucaparib dose is NOT allowed.

Regimen level	Expected probability of toxicity
-1 (300 mg BID)	10%
0 (400 mg BID)	17%
1 (500 mg BID)	24%
2 (600 mg BID)	30%

Doses will be allocated to patients according to the TITE-CRM criterion, as summarized here. Start of the CRM algorithm is dose level 0.

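### Two rules for the last rucaparib day conflict for some patients who restart after a hold, and the rule tied to the end of RT can leave up to 7 on-drug days outside the 70-day DLT window

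*Combined protocol and SAP*

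**What the plan says.** **The rule tied to the end of RT.** Section 9.1 says: "Rucaparib administration will continue for four weeks after the final fraction of RT". Section 1.0 applies this to mastectomy patients without a boost: "rucaparib will be continued for 4 weeks post-RT for a total of 9 weeks". It also gives the range: "rucaparib will continue for 4 weeks post-RT (total of 9-10 weeks depending on whether a boost is used". These statements agree with one another.

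**The rule tied to the start of treatment.** In Table 11B (Section 11.2), the row for uncontrolled Grade 2 toxicity says missed doses are not made up when a patient restarts after a break, and then: "The patient will take Rucaparib until the conclusion of the initially scheduled 10 weeks". Section 9.7 also gives ten weeks, but with an exception: "Treatment is expected to continue for a total of ten weeks (70 days), as described, unless delayed by adverse events".

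**The DLT window.** Section 9.5 counts toxicities "observed during the 70 days that include 6 weeks of radiotherapy and 4 weeks of maintenance rucaparib therapy". Section 14.0 agrees: "The acute observation period for toxicity is defined as 10 weeks, which includes the 6-week rucaparib and radiotherapy treatment course". Sections 4.1, 12.0 and 14.0 allow escalation only after at least two patients have been observed for the full 70 days.

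**RT breaks.** Section 11.2 lets RT be withheld for toxicity "without being considered a dose-limiting toxicity if the treatment break is no greater than 5 days". Section 9.5 sets the DLT threshold at a delay of more than 5 business days. Section 9.2 makes the one-week boost optional after mastectomy.

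**The concern.** Drug exposure has two possible end points, one moving with RT and one fixed from the start, while the DLT window has a single fixed length. They coincide for the standard course of six weeks of RT without a break. They separate when there is no boost or when RT is delayed, and the plan expects both.

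Two things are at stake. First, after a hold and restart, a no-boost patient or a boosted patient with delayed RT cannot be treated according to both Section 9.1 and Table 11B. Sites may resolve this differently, so patients at the same dose level could have different planned exposure.

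Second, Section 9.5 lets only toxicities within the 70 days influence dose assignment. A boosted patient whose RT is delayed and who follows Section 9.1 exactly is still taking drug when that window closes. Her later toxicity is lost to the dose-finding model, and she can count as one of the two fully observed patients needed for escalation while still on treatment. Table 10A is drawn only for the six-week RT course and ends its on-treatment columns at week 10, so an eleventh week of drug has no scheduled column.

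**Working it through.** No sample-size formula applies; the check is calendar arithmetic.

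**Inputs.** RT lasts 6 weeks with a boost or 5 without (Sections 1.0 and 9.2). Rucaparib continues 4 weeks after RT (Sections 1.0 and 9.1). The longest RT delay that is not itself a DLT is 5 business days (Section 9.5), or one calendar week. The window is 70 days (Sections 9.5 and 14.0). I assume the 70 days run from the first fraction.

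**Formula.** Last drug day under the RT-end rule = (RT weeks + delay weeks + 4) × 7.

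**The plan's own figures.** With a boost and no delay, (6 + 0 + 4) × 7 = 70 days, matching Sections 9.5, 9.7 and 14.0. With no boost and no delay, (5 + 0 + 4) × 7 = 63 days, matching the 9 weeks in Section 1.0.

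| Patient | RT-end rule | Table 11B, read literally, if she restarts after a hold | RT-end rule minus 70 |
|---|---|---|---|
| Boost, no RT delay | (6+0+4)×7 = 70 | 70 | 0 |
| No boost, no RT delay | (5+0+4)×7 = 63 | 70 | −7 |
| Boost, 5-business-day delay | (6+1+4)×7 = 77 | 70 | +7 |
| No boost, 5-business-day delay | (5+1+4)×7 = 70 | 70 | 0 |

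**Conflict between the rules.** Columns two and three differ by 7 days in rows two and three, and only for patients who restart after a hold.

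**Mismatch with the window.** This is the last column, and it needs no hold. In row three, 77 − 70 = 7 drug days fall after the window closes. In row two, 70 − 63 = 7 window days (7/70 = 10%) are off drug. Across patients, the RT-end rule gives 63 to 77 days of exposure, a spread of 14 days.

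**Calendar detail.** These are whole weeks, as the protocol counts them. Counting weekdays from the first fraction, a Monday start brings each RT-end date forward by two days. The last drug day is then 61–63 (no boost), 68–70 (boost) or 75–77 (boost with delay), so the overhang in row three is 5 to 7 days.

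**Illustration of scale.** The documents give no hazard shape. Suppose a constant DLT hazard on drug, none off drug, and 30% cumulative risk at 70 days. Then risk is 1 − 0.7^(63/70) = 27.5% at 63 days and 1 − 0.7^(77/70) = 32.5% at 77 days, about 2.5 percentage points either side of the target.

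**The case against.** The strongest reply is that Table 11B is not a general stopping rule. Its sentence sits in one row, covers restart after a rucaparib hold, and evidently means that a hold does not lengthen the course. An RT break alone does not trigger it. This stands, so the conflict between the rules is confined to patients who restart after a hold. It does not touch the overhang to day 77, which follows from Section 9.1 alone.

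A related reply is that the initial schedule means each patient's own schedule, with 10 weeks as shorthand for the standard course. That would remove the no-boost conflict, although the text says 10 weeks. It would not remove the conflict for a boosted patient with both an RT delay and a hold: her initial schedule ends at day 70 and Section 9.1 takes her to day 77.

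A reader might infer that there are three different stop dates and that none matches the window. The documents do not support this. Sections 1.0 and 9.1 state one rule. Table 11B and Section 9.7 both give 70 days, as does the RT-end rule for an uninterrupted boosted course.

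A reader might also infer that DLT observation is shorter for no-boost patients. It is not: the window is 70 days for everyone, so a patient who stops at day 63 loses no on-drug DLT.

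Nor is toxicity after day 70 lost to safety reporting. Section 14.0 tabulates treatment-emergent events to 30 days after the last dose of drug or RT, and Section 17.2 covers serious events. The gap is in the dose-finding data only.

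Finally, matching the window to each patient's own course would be a poor remedy. The 30% target would then refer to 63, 70 or 77 days within a one-parameter model, and no-boost observation could shrink. That objection is sound, and the fix respects it.

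**Conclusion.** The point holds in a limited form and should be corrected. Two rules set the last rucaparib day. For a patient who restarts after a hold, they differ by 7 days if she has no boost, or if she has a boost and a 5-business-day RT delay. Section 9.7 does not settle the matter, because it gives ten weeks but lets adverse events delay the end.

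Independently of any hold, the RT-end rule can leave a boosted patient with delayed RT on drug for up to 7 days after the DLT window closes. Toxicity in those days does not enter the TITE-CRM, and the escalation condition can be met by a patient still on drug. No-boost patients are fully observed but spend the last 7 window days off drug.

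The 7-day figures use whole weeks and the business-day threshold in Section 9.5. Section 11.2 says only days; a 5-day break spanning a weekend would miss as few as 5 − 2 = 3 treatment days and move the end of RT by less.

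The documents do not show that the MTD or any dose assignment would change. They give no expected frequency of no-boost, RT-delayed or hold-and-restart patients.

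**What to change.** 1. Reconcile Sections 1.0, 9.1, 9.7 and Table 11B so that one rule fixes the last rucaparib day for boost, no-boost and interrupted patients. Which rule is right is for the sponsor to decide.
2. Align the 5 days in the opening of Section 11.2 with the 5 business days in Section 9.5.
3. Keep the common 70-day window as the minimum for all patients, and say in Sections 9.5 and 14.0 that it applies to no-boost patients too.
4. If the reconciled rule still allows drug after day 70, state in Sections 9.5 and 14.0 that a qualifying toxicity up to the last protocol rucaparib dose counts as a DLT. State also that the patient is not fully observed for the escalation condition until then.

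Items 1 to 3 cost only wording. Item 4 needs a small change to the dose-assignment script; a few patients would reach full weight up to a week later, and for them the 30% target would cover slightly more than 70 days.

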11.3 Definition of an Adverse Event

An AE is defined as any untoward medical occurrence in a patient administered a medicinal product that does not necessarily have a causal relationship with this treatment. An AE can, therefore, be any unfavorable and unintended sign (including an abnormal laboratory finding), symptom, or disease temporally associated with the use of an investigational product, whether or not related to the investigational medicinal product. This includes an exacerbation of pre-existing conditions or events, intercurrent illnesses, drug interaction, or the significant worsening of the indication under investigation that is not recorded elsewhere. Anticipated fluctuations of pre-existing conditions, including the disease under study, that do not represent a clinically significant exacerbation or worsening are not considered AEs.

It is the responsibility of the investigator to document all AEs that occur during the study. AEs should be elicited by asking the patient a non-leading question (eg, "Have you experienced any new or changed symptoms since we last asked/since your last visit?"). The existence of an AE may be concluded from a spontaneous report of the patient; from the physical examination; or from special tests such as the ECG, laboratory assessments, or other study-specified procedure (source of AE). Symptoms reported spontaneously by the patient during the physical examination would also qualify

as an AE (and hence documented on the AE CRF, not on the physical examination CRF, which is reserved for physical signs or findings).

Refer to **Section 17.2** for details and reporting requirements on Adverse Events, Serious Adverse Events, Events of Special Interest.

12.0 CRITERIA FOR THERAPEUTIC RESPONSE/OUTCOME ASSESSMENT

The primary endpoint of the study is defining the MTD of rucaparib in combination with RT to the breast/chest wall with or without regional nodes.

The trial will be monitored using TITE-CRM, which is described in Section 14.0.

Sample Size

The study will enroll 30 patients who are able to complete the acute observation period without a dose-limiting event, or who experience a DLT for the estimation of the dose-toxicity function. We expect to accrue about 4 patients about every two months, therefore completing accrual in approximately 1-2 years.

Cohort Size

Subjects will be recruited as available and allocated to treatment according to the estimated toxicity rates. No formal cohort size is required; however, at least 2 patients must be observed for their entire acute toxicity period (70 days) before dose escalation is allowed. This rule will be followed throughout the trial.

Endpoint Definition

Locoregional relapse is defined as a recurrence of disease in the breast, chest wall, axilla, supraclavicular or internal mammary areas. Distant relapse is defined as a recurrence of breast cancer in any part of the body outside of the locoregional sites described above (ie bone, liver, brain).

Evaluability

Any subject receiving at least one dose of rucaparib and at least one fraction of RT will be considered evaluable for toxicity. Subjects who do not initiate treatment with either rucaparib or RT will be replaced and will not influence the TITE-CRM dose assignment algorithm. Any subject who discontinues trial therapy after receiving at least one dose of rucaparib and one radiotherapy fraction, but prior to completing the entire course of study treatment for reasons not due to toxicity, will also be replaced. These subjects will not count toward the sample size goal of 30 subjects; however, partial information from discontinuing subjects up until the date of discontinuation will be used by the TITE-CRM algorithm when making dose level assignments. Thus, these subjects' information will NOT be used following the date of discontinuation for future dose assignments. At the trial's conclusion, posterior estimates for the probability of toxicity at each dose level will be

made using only the 30 subjects with complete data (i.e. subjects that complete the acute observation period without a dose-limiting event, or those that experience a DLT).

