As of 8/7/2019, we have accrued 7 out of 30 patients to this trial. Two patients were accrued to dose level 0 (400 mg BID) and 5 to dose level -1 (300 mg BID). Based on the data, dose level -1 has been found to exceed our targeted 30% DLT rate. We have therefore added three additional lower dose levels, one at 200 mg BID (dose level -2), another at 300 mg QD (dose level -3) and a third at 200 mg QD (dose level -4). The revised dose allocation table and revised expected probability of toxicity is provided in the table below. The expected probability of toxicity takes into account accrued data up to 8/7/2019. All the patients will be is determined by the TITE-CRM based on all patient toxicities.

Regimen level	Expected probability of toxicity
-4 (200 mg QD)	20%
-3 (300 mg QD)	30%

-2 (200 mg BID)	40%
-1 (300 mg BID)	50%
0 (400 mg BID)	62%
1 (500 mg BID)	70%
2 (600 mg BID)	76%

- When a patient presents for enrollment on this trial, the probability of toxicity will be estimated for each dose level, based upon the initial expectations of toxicity and the incidence of toxicity in patients already treated, weighted by the amount of time those patients have been followed during the acute observation period. The level that has estimated toxicity closest to the target rate subject to conditions below, will be selected.
- In the extremely rare event a patient is removed from study prior to completing the acute observation period, for reasons unrelated to toxicity, the patient will be considered not to have experienced a DLT event. The patient will contribute her weighted follow-up experience to the estimate of the probability of toxicity up until the date of discontinuation. Her information will not be used following the date of discontinuation.
- The dose level cannot be escalated until at least two patients have been observed for the entire acute toxicity period (70 days). This rule will be followed throughout the trial.
- Dose escalation is restricted to one level between adjacent patients.
- There is no restriction on the number of levels that the dose may be reduced between patients.
- A maximum of 4 patients per calendar month can be enrolled.
- Patients 1 and 2 will be assigned to dose level 0.
- For patients 3 to 15, the dose level estimated to have probability of DLT closest to but not exceeding the target rate, 30%, by more than 5% (i.e. 35% predicted probability) will be assigned to the newly enrolled patients.

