Under the CRM paradigm, the relationship between dose and toxicity is summarized by a single-parameter (α) logistic model that represents the assumed relationship prior to the collection of any patient data. Information about the relationship between dose and toxicity can be summarized using the distribution of the parameter, updated according to the current data. For instance, we can estimate the probability of toxicity at assigned doses and the subsequent target dose as a function of α based on the current data. The toxicity results will be summarized as follows.

The distribution of α updated according to the current data and the corresponding dose-toxicity model will be calculated. Predictive intervals concerning the toxicity parameter will be provided using this updated distribution of α .

The posterior distribution of toxicity, which display the probability a future patient will experience toxicity at a given dose based on the current data, will be calculated for each tested level. The dose level of rucaparib that produces the target rate of toxicity will be determined from this.

The proportion of subjects encountering toxicity at each dose level will be reported.

Analysis of Secondary Endpoints

Toxicity profiles will be tabulated and summarized. Locoregional relapse and distant relapse will be estimated using Kaplan-Meier methods.

Correlations between locoregional and distant relapse with HRD status (deficient vs proficient) and stromal TILs (present vs absent) will be evaluated using Kaplan-Meier estimates and a log-rank test. Patient satisfaction, quality of life, and cosmetic outcomes will be summarized descriptively and graphically. Note, for the cosmesis outcome based on the RTOG scale as provided in the appendix, excellent and good cosmesis will be grouped together, and fair and poor will be grouped together. The rate of fair/poor cosmesis will be calculated and described. All statistical analyses of secondary endpoints are considered to be exploratory in nature as the sample size is expected to be small in this phase I study. Analyses will be done over all 30 patients accrued to the study and by dose cohort.

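### The final posterior for the MTD drops treated patients who leave early without a DLT, which raises the estimated DLT rates slightly if withdrawal is unrelated to toxicity

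*Combined protocol and SAP*

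**What the plan says.** Section 12.0, Evaluability, sets four rules.

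- On who counts for toxicity: "Any subject receiving at least one dose of rucaparib and at least one fraction of RT will be considered evaluable for toxicity".
- Treated patients who stop "prior to completing the entire course of study treatment for reasons not due to toxicity, will also be replaced", and they do not count toward the 30.
- During the trial, "partial information from discontinuing subjects up until the date of discontinuation will be used by the TITE-CRM algorithm when making dose level assignments".
- At the end, posterior DLT probabilities are "made using only the 30 subjects with complete data", which means "subjects that complete the acute observation period without a dose-limiting event, or those that experience a DLT".

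Section 14.0, Dose allocation, covers the same early leavers. If removal is "for reasons unrelated to toxicity, the patient will be considered not to have experienced a DLT event". It adds: "The patient will contribute her weighted follow-up experience to the estimate of the probability of toxicity up until the date of discontinuation". It describes such removals as very uncommon but gives no figure. The later part of Section 14.0 on the details of the TITE-CRM describes the posterior without repeating the restriction to complete patients. The operating characteristics mention neither withdrawal nor the final-analysis rule.

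**The concern.** Entry to the final data set depends on the outcome. A patient with a DLT on day 20 is in. A patient who leaves on day 60 without a DLT is out and is replaced. DLTs get in at any time and non-DLTs only at day 70, so the retained set has too many DLTs. The MTD is the primary endpoint, and it would be read from a posterior that ignores information the algorithm used when it assigned the last patients. TITE-CRM was chosen because it can use partial follow-up.

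**Working it through.** **Inputs from the plan.** Target DLT rate 30%; window 70 days; 30 patients, of whom 23 remained at the amendment; simulated accrual 4 per 70 days; MTD is the level closest to target (all Section 14.0). **Assumptions.** Withdrawal d of 3, 5, 10 or 20%, independent of toxicity and uniform over the window; linear weight (follow-up divided by 70 days); uniform DLT onset unless stated.

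**1. The plan's own figures.** A TITE-CRM simulation without withdrawal (one-parameter empiric model, prior DLT estimates 10/20/30/40%, 3000 trials) selects the true 30% level in 48.5, 40.1 and 44.1% of trials in Scenarios 2, 3 and 4. Table 2 gives 49.4, 40.7 and 43.2%. Scenario 1 does not match (57–61% across model variants against 63.4%); the exact software settings are not stated. Both final analyses below run on the same simulated trials, so this gap does not affect their comparison.

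**2. Direction.** A leaver with weight w, at a level with DLT probability F, contributes a factor 1 − wF to the likelihood. Deleting it moves a one-parameter posterior toward higher toxicity. Every estimated rate rises or stays, so the level closest to 30% falls or stays.

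**3. Size of the rate shift.** Let m be the mean DLT time as a fraction of 70 days. The complete-patient rate tends to

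p(1 − dm) / [p(1 − dm) + (1 − p)(1 − d)].

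With p = 0.30 and m = 0.5:

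- d = 3%: 0.2955 / (0.2955 + 0.679) = 30.3%
- d = 5%: 0.2925 / (0.2925 + 0.665) = 30.5%
- d = 10%: 0.285 / (0.285 + 0.63) = 31.1%
- d = 20%: 0.27 / (0.27 + 0.56) = 32.5%

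Early onset (m = 1/3) gives 30.4, 30.7, 31.5 and 33.3%. Late onset (m = 2/3) gives 30.2, 30.4, 30.8 and 31.7%.

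**4. Effect on the declared MTD.** Leavers are replaced until the target number is complete. Each trial is then analysed twice: complete patients only, and all treated patients with weights (1000 trials per row).

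| Setting | d | Complete-only MTD lower | Higher | Correct selection, complete vs weighted |
|---|---|---|---|---|
| Original Scenario 2, n = 30 | 3% | 2.7% | 0 | 54.2 vs 54.0% |
| | 5% | 5.5% | 0 | 49.9 vs 50.2% |
| | 10% | 12.3% | 0 | 51.8 vs 52.8% |
| | 20% | 21.6% | 0 | 48.7 vs 53.2% |
| Amended Scenario 4, n = 23 | 5% | 5.1% | 0 | 41.2 vs 41.3% |
| | 10% | 10.9% | 0 | 42.0 vs 43.6% |
| | 20% | 23.2% | 0 | 45.0 vs 46.2% |
| Amended Scenario 5, n = 23 | 5% | 4.8% | 0 | 38.5 vs 38.7% |
| | 10% | 10.3% | 0 | 39.4 vs 41.5% |
| | 20% | 19.8% | 0 | 36.0 vs 37.7% |

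Over 13,000 trials with withdrawal, including late-onset, logistic and toxicity-related variants, the complete-only MTD was never the higher one. A repeat of the comparison gave about 4, 9 and 19–23% lower at d = 5, 10 and 20%, with correct selection differing by 0–1 point at 5–10% and by up to about 3.5 points at 20%. The two sets agree within simulation error: with 10.9% discordant trials out of 1000, the standard error of the difference in correct selection is at most √(0.109/1000), about 1 point.

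**The case against.** The strongest reply is that the rule is prespecified, that it uses fully observed patients, and that the plan expects almost no such exits. At 3% withdrawal the shift is 0.3 points, with on average 0.8 leavers per 30-patient trial. This stands, and it is why the point is minor. It does not remove the point: no figure supports the expectation, Section 13.1 lists non-toxicity exits such as patient request and non-compliance, and at 3–5% withdrawal the chance of at least one leaver among the remaining 23 is 1 − 0.97²³ = 50% to 1 − 0.95²³ = 69%.

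Weighting also has its own bias. Linear weights suit uniform onset. With late onset (assumed mean at 75% of the window) and 10% withdrawal, the weighted estimate of a true 30% is about 29.3–29.4%, against 30.6% for complete patients. The two errors are of similar size and opposite sign, which is a reason to show both results.

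Four stronger readings are tempting, and the documents do not support them.

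- **That Sections 12.0 and 14.0 flatly contradict each other.** Section 12.0 itself separates dose assignment from the closing estimate, and the weighted rule in Section 14.0 stands under Dose allocation. Being evaluable for toxicity is compatible with the safety analysis, which tabulates all patients.
- **That the secondary analyses exclude replaced patients.** The plan says "Analyses will be done over all 30 patients accrued to the study and by dose cohort". That is loose if replacement takes the treated number above 30, but it states no exclusion, and these analyses are labelled exploratory.
- **That the bias is upward whatever the reason for leaving.** If 20% of patients heading for a DLT left first, the complete-patient rate would be 0.24 / (0.24 + 0.70) = 25.5%, below the true 30%. Weighted inclusion would be slightly lower still.
- **That the share of trials with a lower MTD is an error rate.** It counts disagreement between two estimators. Correct selection moves far less. Where the lowest level is the right one (amended Scenario 6), the downward push even raises correct selection.

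**Conclusion.** The point holds as a minor one. The final data set is selected by outcome. With withdrawal unrelated to toxicity, which is how both sections define this group, the estimated DLT rates are biased upward. Relative to weighted inclusion, the declared MTD is unchanged or lower. At 3–5% withdrawal the bias is about 0.2 to 0.7 points across the onset patterns tried, and the MTD differs in about 3–6% of trials with almost no change in correct selection. A clear loss appears only near 20% withdrawal, a rate that the plan does not anticipate. The direction relative to weighting follows from the one-parameter model. The sizes rest on assumed withdrawal rates, onset patterns, linear weights and model settings that the plan does not state.

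**What to change.** Replace the closing sentence of Section 12.0, Evaluability, with a rule to this effect: the final posterior uses every patient who received at least one rucaparib dose and one RT fraction; a patient who left without a DLT enters as a non-DLT with her TITE weight frozen at the date of discontinuation; the posterior from the 30 complete patients is reported as a sensitivity analysis. State the weight function, and say in Section 14.0 that the weight is frozen and the patient is not removed, since the present wording allows either reading. Settle this before the MTD is declared, so that the data set is not chosen with the result in view.

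The cost is one or two sentences and a second run of the final model. The weights are already needed for dose assignment, and the enrolment target and dose-assignment rules do not change. The small downside is the slightly low weighted estimate if DLTs come late, which the paired report would make visible.
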